### 2.3.2 KNOWN POTENTIAL BENEFITS

#### Impact on Health Decisions

There is a dire need to establish care delivery systems that can address the opioid crisis in pregnant women. While there are several “ideal” models, a helpful model is one that could be implemented in obstetrical settings alongside prenatal care and would help pregnant women minimize their use of opioids and other substances. Both models outlined above have strengths and weaknesses in this regard. ECHO is scalable and as evidenced by the dramatic success in New Mexico, shows great promise to train obstetrical providers. The development of a “learning community” through the group case

presentation process, is a very powerful way in which to share knowledge and enhance therapeutic confidence among providers. This can go beyond clinical issues of medication initiation and titration to include ways to improve referral systems. Depending upon the commitment of the practice and their willingness to share resources, multiple individuals can be trained, and this can include physicians and support staff. The potential down-side of ECHO is the time-crunch physicians experience. While each practice can dedicate staff duties as it would desire, there is no explicit CM role in the ECHO model. In this sense, ECHO may have a greater impact in settings where some extender activities are already available (e.g. social worker services, recovery coaches, advanced practice nurses) although this is not clear. In addition to extender concerns, members of the team in the practice who plan to participate in ECHO (in this case physicians and nurses), must make time and be available to attend the ECHO sessions and to share case information with their colleagues. Availability can be a challenge in busy obstetric settings not only because of issues of patient flow but because of obstetrical emergencies.

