#### Protection Against Risks

To minimize risks associated with study participation, we will take the following steps: First, designated staff person or care managers will tell potential participants that some assessment questions focus on sensitive topics and they can always choose not to answer a specific question. If a participant is upset by survey content, or develops suicidal ideation, the care manager can locate appropriate clinic staff or study staff to assist with the situation. We will train research staff to identify severe psychological distress and under those circumstances will inform a senior member of the research team to determine the safest course of action. We will also include a rescue protocol for worsening opioid or other substance use or suicidal ideation. This may include inpatient or partial hospitalization. Study faculty are experienced in the management of such circumstances with patient safety of paramount importance. We will tell participants that their clinical data are confidential and protected under HIPAA. We will link research data only by a participant ID number. We will collect survey data by computer using REDCAP®, a secure, encrypted program that affords additional protection of confidentiality for study participants. To further protect pregnant women participating in this research, we will obtain a Federal Certificate of Confidentiality. In addition, women will be told their decision to participate in the study is voluntary. They can choose not to participate or they can choose to withdraw from the study at any time, and it will not adversely affect their care at the clinic.

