Potentially eligible women will also be given the option of having a researcher contact them by phone and reviewing the consent via phone or Yale Zoom if that is their preference. In this scenario, women will provide verbal consent to the DSP at the practice site if they are interested in being contacted by study staff, and the obstetrical provider will provide her name and contact information to research staff. Referred women will be contacted by phone or by a research assistant who will explain the entire protocol and all of its requirements at length. Additionally, women are encouraged to ask questions about any confusing points. Subjects are told that they may withdraw from the project at any time, without prejudice, and without any adverse effect on their medical care at their prenatal clinic. Women who express interest in study participation will be emailed or texted a link of the study consent form using REDCap@yale. Participants will be provided with time to review the content and the researcher will then review the eConsent form, and answer any remaining questions. Once the participant has signed and submitted the eConsent form the research assistant will receive a REDCap notification of its submission and will review the form to confirm it is filled out correctly. The research assistant will then open the corresponding 'Person Obtaining Consent' form as a survey and electronically sign it. Screening and baseline assessments as described above will then be emailed or texted to the participant.

After enrollment, a urine drug screen (UDS) will be obtained at each prenatal visit (the urine will be collected as part of the regular prenatal visit and tested for the presence of illicit and licit opiate drugs). Study sites will be asked to report results of UDS by completing a form that is entered into REDCap. Participants will also be contacted monthly by a Yale research assistant (who is blind to condition) to complete a **Time Line Follow-Back (TLFB)** and the **Treatment Utilization Form** that includes questions about the quantity and frequency of all substances used and treatment received. Study participants will complete additional self-report questionnaires at the following assessment points: enrollment, 26 weeks

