#### Rescue Protocol for Suicidal Ideation

- 1) If a participant endorses greater than "0" on the Edinburgh Postnatal Depression Rating Scale question # 10, the tablet will be programmed to have a hard stop. The participant will be instructed to show the scale to their nurse or doctor so that sites can employ their usual procedures to further assess suicide plans or intent and manage the patient (eg. assessment by a behavioral health care provider or referral to the emergency department)
- 2) Study personnel will work with sites that do not have a pre-existing suicide protocol to develop such a plan

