## 8 STUDY ASSESSMENTS AND PROCEDURES

### 8.1 ENDPOINT AND OTHER NON-SAFETY ASSESSMENTS

#### 8.1.1 SCREENING & BASELINE PROCEDURES

- Substance Misuse Screen – All patients seen at the participating clinical are asked substance misuse screening questions as part of their standard of care. Patients who answer affirmatively will be approached for consent.
- Demographics- Consented patients will have demographic data collected including information about pregnancy dates, medications and complications.
- Concomitant Therapy- Participants will be asked about any medications or other therapy they have received since their last visit. This information will be recorded in the eCRF.
- Medical History- Participants will be asked about their medical history. Medical history will also be collected through review of the patient's medical record if available.
- Pregnancy Questionnaire- The following information will be collected about the patient's current pregnancy; dates, medications and complications
- Urine Drug Screening- Urine collected at pre-natal visit will be tested for illicit drugs and licit opioids
- DSM-5 OUD Checklist- Patient's will complete the DSM-5 OUD checklist to confirm OUD.
- Contact Information- At least 3 verified locators will be collected for each participant. If available, one of these contacts will be a significant other who can provide collateral information and maintain subject involvement
- Self-Assessments Including:
  - Patient Activation Measure (PAM)
  - Post Traumatic Stress Disorder Checklist for DSM-5 (PCL-5)

- *Fagerstrom Test For Nicotine Dependence (FTND)*
- *HIV Risk Taking Behavior Scale (HRBS)*
- *Shared-Decision Making Questionnaire-9 (SDM-Q-9)*
- *Perceived efficacy in Patient-Physician Interactions Questionnaire (PEPPI)*
- *Kim Alliance Scale-Communication subscale (KAS-CM)*
- *PROMIS Emotional Short Form*
- *Satisfaction with Roles and Activities*
- *Edinburgh Postnatal Depression Scale (EPDS)*
- *Stigma Related Rejection Scale*
- *Adverse Childhood Experience Questionnaire*

---

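### For an EPDS completed by emailed or texted link, the protocol specifies no alert, responsible person or call when the suicide item is positive

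*Combined protocol and SAP*

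**What the plan says.** The Rescue Protocol for Suicidal Ideation (Section 6.5.1) acts on any EPDS item 10 score above 0. At that point "the tablet will be programmed to have a hard stop", and "The participant will be instructed to show the scale to their nurse or doctor so that sites can employ their usual procedures". Study personnel help sites that have no suicide plan to write one.

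Section 4.1 describes two ways to enroll. In the clinic, a designated staff person hands the woman a tablet. Alternatively, a research assistant contacts her, reviews consent by phone or Zoom and sends an eConsent link. When the consent form comes back, "the research assistant will receive a REDCap notification of its submission". The same paragraph ends: "Screening and baseline assessments as described above will then be emailed or texted to the participant". The EPDS is marked at screening in the Schedule of Activities (Section 1.3) and listed in Section 8.1.1 among the screening and baseline self-assessments.

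Other text places the enrollment battery with site staff. Section 4.1 goes on to list the questionnaire time points, enrollment among them, and says a staff-provided tablet is used. Section 6.1.1 has the collaborative care (CC) care manager ask for the battery at enrollment. Section 6.1.2 has the ECHO staff person hand over a tablet at enrollment.

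**The concern.** The written response to a positive item 10 depends on the participant showing a screen to a clinician. That suits a woman holding a clinic tablet. A woman who opens a link elsewhere may have no clinician with her, and the protocol gives staff no other way to learn of her answer promptly.

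What is at stake is her safety. Section 2.3.3 gives suicidal ideation as an example of the clinical worsening it regards as common among these women. A study that asks the question should say what happens to the answer on every route it offers.

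**Working it through.** The protocol gives no figure to reproduce, so the check sets the relevant sections side by side.

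1. **Trigger and action (Section 6.5.1).** The trigger is item 10 above 0. The device named is a tablet, and the action is taken by the participant. Site procedures follow from her action.

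2. **Delivery on the remote route (Section 4.1).** Screening and baseline assessments are emailed or texted after remote consent. The phrase about assessments already described points back to the clinic-route paragraph, which includes the additional Visit 1 baseline questions. With Sections 1.3 and 8.1.1, the natural reading is that the EPDS is among the forms sent.

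3. **Conflicting text.** Later in Section 4.1, and in 6.1.1 and 6.1.2, enrollment questionnaires are a site-staff task, with a tablet named in 4.1 and, for ECHO, in 6.1.2. Nothing says which text governs a woman who consents remotely.

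4. **Notifications.** The only automatic staff notification described for the remote route is for submission of the consent form. None is described for item 10.

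5. **Do other safeguards cover a positive answer given by link?**
   - Section 2.3.3: if a participant is upset by the survey or "develops suicidal ideation, the care manager can locate appropriate clinic staff or study staff to assist with the situation". This needs a care manager who knows. Section 2.3.2 adds that "there is no explicit CM role in the ECHO model".
   - Section 2.3.3: "We will train research staff to identify severe psychological distress", who then inform a senior team member. This needs contact, and no live contact is stated while the link is completed.
   - Section 2.3.3: 4 psychiatrists are available for support, but no item 10 result is routed to them.
   - Section 6.1.1: the safety transfer procedure for a suicidal patient is a CC care manager duty and begins once the care manager knows.
   - Section 6.5.1: practice rescue protocols begin once the practice knows.
   - Sections 5.5 and 8.2: the first visit is to be scheduled quickly and adverse events are asked about at each contact. Neither sets a time limit or calls for review of item 10.

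   Every safeguard starts after someone is aware. None makes anyone aware.

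6. **Size.** The documents give neither the share of women completing baseline by link nor the prevalence of item 10 above 0. Suppose, as pure assumptions, that 5% to 50% of the 264 women do so and 2% to 20% of them are positive:
   - Low corner: 264 × 0.05 ≈ 13 women; 13 × 0.02 = 0.26 positives.
   - High corner: 264 × 0.50 = 132 women; 132 × 0.20 = 26.4 positives.

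   The ratio is 26.4 / 0.26 ≈ 100. So wide a range shows only that the number is unknown. It also counts positive answers on the route, not answers left unattended.

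**The case against.** The best reply is that the protocol does not settle whether any EPDS is completed by link. Enrollment is one of the time points for which Section 4.1 names a staff-provided tablet, and Sections 6.1.1 and 6.1.2 agree. This stands in part. A reader might infer that every remote enrollee receives the baseline EPDS by email or text; the text supports that as one reading of conflicting provisions. The conflict is itself a reason to clarify, because a site following the emailed-link sentence would have no workable step for item 10. A reader might also use the tablet sentence to confine the gap to baseline. It cannot carry that weight: if it does not bind at enrollment, it is no firm assurance for later visits.

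Second, staff contact may be close at hand. The notes to Section 1.3 put Visit 1 immediately after consent, and the research assistant has just been speaking with her. Sections 5.5 and 8.1.1 also collect several verified contacts. This makes prompt follow-up feasible but does not require it.

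Third, site suicide plans, the study SOP and the REDCap build are not among the documents and may already hold an alert. That stands: what is shown is silence in the protocol, not proof that no procedure exists.

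Fourth, it would be too strong to say she cannot follow the instruction. Women referred by a site are prenatal patients with a clinic they can contact. The supportable statement is that the plan depends on her doing so unprompted by staff.

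Fifth, there is little time left for a prospective change to help. The current text postdates 1.30.24 (Section 9.4.2), and Section 5.1 requires gestation under 34 weeks and delivery by July 1, 2024. Taking that as a 40-week due date, enrollment ends about 40 − 34 = 6 weeks earlier, around May 20, 2024. This limits the forward benefit but not the value of checking forms already completed.

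**Conclusion.** The point holds for any EPDS completed by link. The protocol offers a route on which its written response to a positive item 10 may not reach staff, and it names no alert, responsible person or call for that case. A positive answer may go unseen until the next contact. That no clinician is present is an inference from email or text delivery, though a reasonable one.

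The number of women affected is unknown, and the argument does not rest on the illustrative counts. The documents do not support a claim that women were left without help, or that no procedure exists outside the protocol. This is a participant-safety and operations matter rather than an analysis choice. It should be fixed; confidence is medium because the operational documents are unseen.

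**What to change.** In Sections 6.5.1 and 4.1, state that any EPDS completed off site is either done while the research assistant is on the call or deferred to the first clinic visit.

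If neither is practicable:
- Program a REDCap alert on item 10 above 0 to an existing study clinician and to the site. It should not go to the assistant doing the monthly Time Line Follow-Back, who is blinded to condition.
- Require a same-day call using contact details already collected (Sections 4.1, 5.5 and 8.1.1).
- On the remote screen, replace the instruction to show a nurse or doctor with immediate contact and crisis information.

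In either case, check remote baselines already completed for item 10 above 0 without documented contact. If an SOP already covers this, one sentence citing it is enough.

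The cost is a short protocol edit and, for the alert, one setting on a platform that already notifies staff of consent. The 4 psychiatrists on the research team could take the alerts, so no new on-call rota is needed. The downsides are some clinician time, false alerts and perhaps less candid answers. Deferral would move some baseline EPDS scores later, which touches only an exploratory outcome.

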## 7 STUDY INTERVENTION/EXPERIMENTAL MANIPULATION DISCONTINUATION AND PARTICIPANT DISCONTINUATION/WITHDRAWAL

### 7.1 PARTICIPANT DISCONTINUATION/WITHDRAWAL FROM THE STUDY

Participants are free to withdraw from participation in the study at any time upon request. An investigator may discontinue a participant from the study for the following reasons:

- Lost-to-follow up; unable to contact subject
- Any event or medical condition or situation occurs such that continued collection of follow-up study data would not be in the best interest of the participant or might require an additional treatment that would confound the interpretation of the study
- The participant meets an exclusion criterion (either newly developed or not previously recognized) that precludes further study participation

The reason for participant discontinuation or withdrawal from the study will be recorded in the CRF.

### 7.2 LOST TO FOLLOW-UP

A participant will be considered lost to follow-up if he or she fails to return for at least three visits scheduled visits and study staff are unable to contact the participant after at least 3 attempts.

The following actions must be taken if a participant fails to return to the clinic for a required study visit:

- The site will attempt to contact the participant, reschedule the missed visit within three weeks, counsel the participant on the importance of maintaining the assigned visit schedule and ascertain if the participant wishes to and/or should continue in the study
- Before a participant is deemed lost to follow-up, the investigator or designee will make every effort to regain contact with the participant including email, text and telephone contact (depending upon patient preference). If a participant does not respond to email, we will attempt 3 telephone calls and, if necessary, a certified letter to the participant's last known mailing address or local equivalent methods). If the participant responds but does not respond again, this will reset the attempts to contact unless she has asked us not to contact her. These contact attempts will be documented in the participant's medical record or study file.
- Should the participant continue to be unreachable, he or she will be considered to have withdrawn from the study with a primary reason of lost to follow-up

## 8 STUDY ASSESSMENTS AND PROCEDURES

### 8.1 ENDPOINT AND OTHER NON-SAFETY ASSESSMENTS

#### 8.1.1 SCREENING & BASELINE PROCEDURES

- Substance Misuse Screen – All patients seen at the participating clinical are asked substance misuse screening questions as part of their standard of care. Patients who answer affirmatively will be approached for consent.
- Demographics- Consented patients will have demographic data collected including information about pregnancy dates, medications and complications.
- Concomitant Therapy- Participants will be asked about any medications or other therapy they have received since their last visit. This information will be recorded in the eCRF.
- Medical History- Participants will be asked about their medical history. Medical history will also be collected through review of the patient's medical record if available.
- Pregnancy Questionnaire- The following information will be collected about the patient's current pregnancy; dates, medications and complications
- Urine Drug Screening- Urine collected at pre-natal visit will be tested for illicit drugs and licit opioids
- DSM-5 OUD Checklist- Patient's will complete the DSM-5 OUD checklist to confirm OUD.
- Contact Information- At least 3 verified locators will be collected for each participant. If available, one of these contacts will be a significant other who can provide collateral information and maintain subject involvement
- Self-Assessments Including:
  - Patient Activation Measure (PAM)
  - Post Traumatic Stress Disorder Checklist for DSM-5 (PCL-5)

- *Fagerstrom Test For Nicotine Dependence (FTND)*
- *HIV Risk Taking Behavior Scale (HRBS)*
- *Shared-Decision Making Questionnaire-9 (SDM-Q-9)*
- *Perceived efficacy in Patient-Physician Interactions Questionnaire (PEPPI)*
- *Kim Alliance Scale-Communication subscale (KAS-CM)*
- *PROMIS Emotional Short Form*
- *Satisfaction with Roles and Activities*
- *Edinburgh Postnatal Depression Scale (EPDS)*
- *Stigma Related Rejection Scale*
- *Adverse Childhood Experience Questionnaire*

---

#### 8.1.2 STANDARD OF CARE PRENATAL VISIT

- Assigned OUD Treatment- Physicians and clinical staff will follow the treatment plan for their assigned group (CC or ECHO) at each patient visit.
- Urine Drug Screening- Urine collected at pre-natal visit will be tested for illicit drugs and licit opioids.

---

#### 8.1.3 TIMELINE FOLLOW BACK VISITS

- Timeline Follow Back- Participants will also be contacted monthly by a research assistant (who is blind to condition) to complete a Time Line Follow-Back (TLFB) about the quantity and frequency of all substances used and treatment received.
- Treatment Utilization Form- Participants will be asked about any medications or other therapy they have received since their last visit.

---

#### 8.1.4 WEEK 26 VISIT

- Self-Assessments Including:
  - *Patient Activation Measure (PAM)*
  - *Fagerstrom Test For Nicotine Dependence (FTND)*
  - *Shared-Decision Making Questionnaire-9 (SDM-Q-9)*
  - *Perceived efficacy in Patient-Physician Interactions Questionnaire (PEPPI)*
  - *Kim Alliance Scale-Communication subscale (KAS-CM)*
  - *PROMIS Emotional Short Form*
  - *Satisfaction with Roles and Activities*

- *Edinburgh Postnatal Depression Scale (EPDS)*
- *Qualitative Interviews (sub group)*

---

## 8.1.5 WEEK 36 VISIT

- *Self-Assessments Including:*
  - *Patient Activation Measure (PAM)*
  - *Fagerstrom Test For Nicotine Dependence (FTND)*
  - *Shared-Decision Making Questionnaire-9 (SDM-Q-9)*
  - *Perceived efficacy in Patient-Physician Interactions Questionnaire (PEPPI)*
  - *Kim Alliance Scale-Communication subscale (KAS-CM)*
  - *PROMIS Emotional Short Form*
  - *Satisfaction with Roles and Activities*
  - *Edinburgh Postnatal Depression Scale (EPDS)*

## 8.1.6 BIRTH

- *Birth Outcomes-* Birth outcomes will be collected through review of the patient's medical record including low birth weight, resuscitation at delivery, fetal demise, preterm birth, duration of hospitalization.

---

## 8.1.7 3 MONTHS POST-PARTUM VISIT

- *Self-Assessments Including:*
  - *Patient Activation Measure (PAM)*
  - *Fagerstrom Test For Nicotine Dependence (FTND)*
  - *Shared-Decision Making Questionnaire-9 (SDM-Q-9)*
  - *Perceived efficacy in Patient-Physician Interactions Questionnaire (PEPPI)*
  - *Kim Alliance Scale-Communication subscale (KAS-CM)*
  - *PROMIS Emotional Short Form*
  - *Satisfaction with Roles and Activities*
  - *Edinburgh Postnatal Depression Scale (EPDS)*
  - *Stigma Related Rejection Scale*
- *Qualitative Interviews (sub group)*
- At 3 months post-partum interviews will be conducted on approximately 20-30 randomly selected patients. Questions on the interview will be regarding the patients' knowledge and experience with Child Protective Services (DCF). Consent for interviews will be

obtained using a verbal consent which will be read to providers prior to beginning the audiorecording. Verbal consent will be used in lieu of written consent as a signed consent would be the only PHI linking the patient to the transcript. Interviews will be audiorecorded and identified by a subject number only. Interviews will be transcribed and any identifying information pertaining to the patient or the clinic at which they receive obstetrical care will be removed. Upon completion of transcription, audiorecordings will be destroyed. All notes, audio recordings and transcriptions will be stored in YaleBox, a password protected, secure cloud storage system. Only members of the study team will have access to this system. Compensation for interviews will be a \$50 Amazon egift card.

